#### 8.4. Responsibilities

CI / delegate:

• Clinical oversight of the safety of patients participating in the study, including an ongoing review of the risk/benefit.

#### 9. STATISTICS AND DATA ANALYSIS

#### 9.1. Sample size calculation

This study will generate neoantigen profiles of oesophageal adenocarcinomas and determine the feasibility of identification of neoantigens by the direct analysis of the tumour ligandome using MS and evaluate neoantigens as targets for future cancer immunotherapies including vaccine-based strategies. Characterisation of the neoantigen profiles of oesophageal or gastroesophageal junction adenocarcinomas is the primary objective of this study which to our knowledge this has not been investigated to any significant extent previously. Gastroesophageal adenocarcinomas are recognised as being genomically heterogeneous and this is likely to be reflected in the heterogeneity of their neoantigen profiles between patients. In this context and at this stage in the investigational process, it is not possible to perform a formal sample size calculation. Nevertheless it is important that the cohort of patients in whom neoantigen profiles will be determined is sufficiently representative to account for expected between patient heterogeneity; provide a clinically useful estimate of the possible frequencies of different neoantigen targets in patients (to guide the future development of personalised cancer vaccine strategies); to provide a useful estimate of the feasibility of our approach to determine neoantigen profiles in individual patients tumours; and be feasible to recruit within a timeframe that is useful to the development of the programme of research with regard to subsequent use to the information generated in this study to develop new therapies and meet the unmet clinical need to develop improved treatments for gastroesophageal cancer. Based upon these considerations, we estimate that analysis of 75 samples (50 oesophageal samples/25 lower oesophageal-gastric junction samples) will be sufficient to determine the feasibility of this method and considering will allow a clinically useful representative profile of neoantigen expression in this tumour type to be undertaken to identify candidate targets for further investigation for cancer immunotherapy. This study will also determine the feasibility of our

assay and method for neoantigen determination in clinical practice and inform the design of , including providing the data needed for sample size calculations for future studies.

## 9.2. Planned recruitment rate

75 participants over 12 months.

## 9.3. Statistical analysis plan

A detailed statistical analysis plan will be developed prior to commencement of the analysis of study data. Outcome analysis will be undertaken once all patient samples have been collected and LC-MS/MS immunopeptidome analysis completed and raw MS data generated for subsequent processing. The outcome analysis will be performed by the CI, their research team, trial scientific adviser and Platinum Informatics Ltd.

## 9.3.1. Primary outcome analysis

The primary outcome is to generate neoantigen profiles of oesophageal adenocarcinomas in individual patients. This will be achieved by analysing the MHC-associated 'immunopeptidome', using a liquid chromatography-tandem mass spectrometry (LC-MS/MS)-based method for direct neoantigen identification with proprietary software tool DESIMAL, created by Platinum Informatics Ltd. This will establish an automated pipeline for raw MS data processing and downstream data interpretation. This outcome of this analysis is qualitative and will describe the detail of the neoantigen expression profile in oesophageal adenocarcinoma.

## 9.3.2. Secondary outcome analysis

The feasibility of neoantigen identification with the described approach in gastroesophageal adenocarcinoma patients, using routinely available clinical biopsy materials will be evaluated by assessing the proportion of patients in whom neoantigens are identified. The minimal amount of oesophageal adenocarcinoma tissue, and the qualitative and quantitative histological features associated with successful neoantigen identification will be evaluated to provide data on the features of optimal tumour specimens for future trials. Characterisation of pre-existing T cell responses to identified neoantigens will enhance evaluation of their potential utility as therapeutic targets for adoptive T cell and/or cancer vaccine approaches for the treatment of oesophageal adenocarcinoma. An exploratory analysis of the relationship between tumour neoantigen profiles and objective response rate, progression free and overall survival will be undertaken.

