#### 2.1. Table of endpoints/outcomes

Primary Objective:	Outcome Measure:	Timepoint
To characterise neoantigen profiles of oesophageal or gastroesophageal junction adenocarcinomas	Neoantigen profiles for individual patients with oesophageal or gastroesophageal junction adenocarcinomas	End of study

Secondary Objectives	Outcome Measures	Timepoint	
1- To determine the feasibility of neoantigen profiling using tumour biopsies of oesophageal or gastroesophageal junction adenocarcinomas	
 
Proportion of patients in which neoantigen profiles are successfully generated
 
	1- End of study	
2- To identify oesophageal or gastroesophageal junction adenocarcinoma neoantigens as candidate targets for immunotherapy	
 
Characterise pre-existing
 
T cell responses to
 
identified neoantigens
 
	2- End of study	
3- To investigate the relationship between neoantigen profiles and clinical outcomes	3- Correlate objective response rate, disease control rate, progression free survival and overall survival with neoantigen profiles.	3- End of study	
4- Recovery of RNA and DNA from samples	
 
Genomic and transcriptomic studies; neoantigen validation experiments.
 
	4- End of study	

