### 6.2. Consent

The PI retains overall responsibility for the conduct of research at their site and this includes taking of informed consent at each site. They must ensure that any person delegated responsibility for seeking informed consent is duly authorised, trained, and competent according to the approved protocol and principles of GCP.

Participants will receive a copy of the Participant Information Sheet (PIS) and will be given at least 24 hours to consider participation in the study prior to consent. Prior to consent participants will be given the opportunity to ask any questions about the study. Where a participant requests to speak with a physician from the study team the consent process will not be completed until the participant has spoken to the physician and had all questions answered to their satisfaction. Once a patient agrees to participate, written informed consent will be obtained and eligibility confirmed.

At time of consent participants will be asked if they only consent to give tissue samples when this is feasible during standard clinical procedures or, where this is not possible, if they give consent to have a biopsy solely for the purpose of obtaining research samples.

Participants may provide additional consent for further biopsies to be taken during further routine clinical care procedures as an optional part of the study.

Written informed consent will be obtained from participants for blood and tissue collection as well as for genomic analysis of these specimens.

The original Informed Consent Form (ICF) will be filed in the TMF or Investigator Site File (ISF), a copy will be given to the participant and a further copy will be filed in the participant's medical notes.

For adults who lose capacity their previous wishes will remain valid unless the protocol changes significantly. If this occurs and further consent is required from a participant who has lost capacity, an appropriate person will be asked for their consent. This will be fully documented in the patient's notes. Data or tissue already collected with consent will be retained and used in the study.

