#### Biopsy

- A fresh tumour biopsy will be collected:
  - Prior to the commencement of any subsequent scheduled anticancer treatments\*;
     OR
  - After the completion of the latest line of anticancer treatment\*; OR
  - During follow up when a participant is not receiving or is between scheduled anticancer treatments\*.

\*Anti-cancer treatments excluding surgery

- The biopsy may be obtained from any site of tumour, primary or metastatic as considered the most appropriate and feasible at the time of the procedure.
- Biopsies from more than one tumour site may be obtained at the same time point and procedure, but this is not mandatory, only biopsy of a single tumour site is required for study participation.
- Up to 10 biopsies, approximately 2mm each, will be taken at each timepoint and if tumour biopsy is being undertaken by endoscopy 2 biopsies approximately 2mm each of adjacent normal oesophageal or gastric mucosa.
- As far as possible, tumour biopsies for the study will be obtained during routine clinical care procedures e.g. endoscopy, surgery, stenting. However, where this is not possible, consent will be requested for study specific procedures for biopsy to obtain tumour material.
- Participants may provide additional consent for further biopsies during further routine clinical care procedures to be taken as an optional part of the study.
- Details of sample collection, processing, storage and transfer will be provided in PROTEAN Clinical Sample Handling Manual.

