#### Justification:

The main risk for participants is from the biopsy of tumour tissue. Where possible this will be done at the same time as standard care biopsy or tumour resection.

What are the key risks related to assessments you plan to undertake in this study?			
Intervention	Hazard	How will these risks be minimised?	
Blood samples	Discomforts of drawing blood include temporary discomfort from the needle stick, the possibility of pain or bruising at the site of the blood draw, occasional feelings of light headedness and, rarely, infection at the site of the blood draw	Blood samples will be taken at the same time as blood draw for routine care purposes whenever possible. Staff taking blood will be experienced in venepuncture.	
Biopsy	Risk of serious complications, such as bleeding, pneumothorax, infection, or even death, depending on the site of disease. Risks vary according to the technical aspects of the biopsy (e.g. size of needle and location or size of the required specimen), the experience or training of the medical professional performing the biopsy, and participant characteristics. The risks for both major complications and AEs increase with multiple biopsies.	Previously collected samples will be used when available, or samples will be taken at the same time as clinically indicated procedures whenever possible. In other instances, the biopsies will be only performed if the risk to the participant is low or moderate. Only samples at baseline are required as per protocol, other samples will only be collected as far as possible during standard care procedures. In considering the study design we have reflected upon the key ethical guidance on research biopsies in cancer research provided in the American Society of Clinical Oncology Research Statement: Ethical Framework for Including Research Biopsies in Oncology Clinical Trials. Journal of Clinical Oncology 37, no. 26 (September 10,	

	2019)2368-2377. Our approach in this study is consistent with this guidance and accordingly is consistent with the practice of oncology studies of this type in a global context.
Outline any other processes that have been put in place (e.g. DMC, independent data review, etc.) Nil	to mitigate risks to participant safety

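### Feasibility is stated for routinely available clinical biopsy material, but the single proportion also admits biopsies done solely for research; separately, section 6.4 and Appendix 1 disagree on stored samples

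*Protocol*

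**What the plan says.** **The claim.** Section 9.3.2 of the protocol says that feasibility "using routinely available clinical biopsy materials will be evaluated by assessing the proportion of patients in whom neoantigens are identified". The introduction to section 2 and section 9.5 tie feasibility to the same kind of material.

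**The endpoint.** The table in section 2.1 defines one measure, "Proportion of patients in which neoantigen profiles are successfully generated", with no split by how the tissue was obtained. Section 9.4 includes all samples of sufficient quality. Section 9.5 counts processing failures in the feasibility result.

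**The tissue admitted.** Section 6.4 makes routine procedures the default: "As far as possible, tumour biopsies for the study will be obtained during routine clinical care procedures". It names endoscopy, surgery and stenting as examples. It continues: "However, where this is not possible, consent will be requested for study specific procedures for biopsy to obtain tumour material". Section 6.2 confirms this, since participants are asked "if they give consent to have a biopsy solely for the purpose of obtaining research samples". No limit is set on the share of such biopsies.

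**Fresh or stored.** Section 6.4 says "A fresh tumour biopsy will be collected" and lists the permitted times relative to anticancer treatment. The risk table in Appendix 1 says "Previously collected samples will be used when available".

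**The concern.** A participant for whom no routine procedure could supply tissue, and who was biopsied only for the study, would count as a success for routinely available material. Section 9.1 says the study will determine feasibility in clinical practice and inform the sample size of later studies. A reader will therefore take the rate as what a clinic can expect from tissue obtained in ordinary care. A rate weighted by an unplanned mix of sources does not carry over to another setting unless success is the same in each source.

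The second problem is a plain contradiction. If stored samples may be used, they enter both the primary profile set and the feasibility denominator, possibly from outside the treatment windows of section 6.4. If they may not, Appendix 1 describes a risk-reduction measure that the study procedures give no means of using.

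**Working it through.** **Planned size.** Section 9.1 sets 75 samples by judgement and says that no formal calculation is possible. The only figure to reproduce is 50 + 25 = 75, which agrees. The protocol states no target rate, precision, source shares or success rates, so everything numerical below rests on assumed inputs.

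**Step 1: claim against population.**

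| Element | Where | Routine tissue only? |
|---|---|---|
| Feasibility claim | Sections 2 (introduction), 9.3.2, 9.5 | Yes, as worded |
| Formal objective and endpoint | Study summary, section 2.1 | No, tumour biopsies in general |
| Permitted sources | Sections 6.2, 6.4 | No, study-specific procedures allowed, no cap |
| Analysis population | Section 9.4 | No restriction by source |

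The narrative claim is narrower than the population that feeds the proportion.

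**Step 2: how far the pooled rate can move.** Let f be the share of samples from study-specific procedures, p_r the success rate in routine-procedure samples and p_s the rate in study-specific samples.

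Pooled rate = (1 − f)·p_r + f·p_s, so pooled − routine = f·(p_s − p_r).

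Pooled rate, with the difference from the routine rate in points:

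| f | p_r 60%, p_s 80% | p_r 50%, p_s 80% | p_r 60%, p_s 70% | both 70% |
|---|---|---|---|---|
| 10% | 62% (+2) | 53% (+3) | 61% (+1) | 70% (0) |
| 20% | 64% (+4) | 56% (+6) | 62% (+2) | 70% (0) |
| 30% | 66% (+6) | 59% (+9) | 63% (+3) | 70% (0) |
| 50% | 70% (+10) | 65% (+15) | 65% (+5) | 70% (0) |

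If study-specific samples do worse, the sign reverses. With p_r = 80%, p_s = 60% and f = 20%, the pooled rate is 0.8 × 80% + 0.2 × 60% = 76%, which is 4 points too low.

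**Step 3: could the data show that pooling is harmless?** For 60% against 80% with 75 samples in total (two-sided 5% test, normal approximation), power is 0.15 at f = 10%, 0.28 at 20%, 0.38 at 30% and 0.47 at 50%. A non-significant comparison between sources would not justify pooling.

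**Step 4: cost of reporting the routine rate.** Exact (Clopper-Pearson) 95% intervals at an assumed rate of about 60%:

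| Denominator | Successes | 95% CI | Width (points) |
|---|---|---|---|
| All 75 | 45 | 48.0% to 71.1% | 23.1 |
| 60 routine | 36 | 46.5% to 72.4% | 25.9 |
| 50 routine | 30 | 45.2% to 73.6% | 28.4 |
| 37 routine | 22 | 42.1% to 75.2% | 33.1 |

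The routine-procedure estimate is less precise but still usable.

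**Step 5: fresh against stored.** The inclusion criteria in section 5.1 require a sample as set out in section 6.4, and that section describes only a fresh biopsy. Section 6.2 offers tissue taken during standard procedures or a research-only biopsy, and mentions no earlier sample. Appendix 1 alone says earlier samples will be used. The passages cannot all be followed when an earlier sample exists.

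**The case against.** The strongest reply is that the formal objective, in the study summary and section 2.1, speaks only of tumour biopsies. On that wording the population is right and the routine qualifier is loose narrative. This stands in part: the endpoint itself is not wrong. But the qualifier appears in three places, including the analysis section and the missing-data section, and those passages say what the rate is evidence for.

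A second reply is that a split by source belongs in the statistical analysis plan, which is not shown, and that the Clinical Sample Handling Manual may record source. Both may be true, and a missing subgroup table is not the complaint. The mismatch lies in the protocol's own wording. The data items in section 6.4 do not list sample source, and sections 6.3 and 10.1 restrict collection to what the study needs, so it is safer for the protocol to ask for it.

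A third reply is that section 9.3.2 already examines tissue amount and histology, through which source might act, and that section 6.4 sets the same allowance for every procedure: "Up to 10 biopsies, approximately 2mm each, will be taken at each timepoint". This weakens any presumption that success differs by source, but it does not establish equality.

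Stronger readings are tempting, and the protocol does not support them:

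- A reader might infer that surgical specimens are not routine. Section 6.4 lists surgery among routine care procedures.
- A reader might infer that taking up to 10 pieces makes even routine-procedure samples non-routine. The protocol never promises leftover diagnostic tissue, and a routine-procedure rate would contain the same sampling.
- A reader might infer that stored samples are part of the cohort. They appear only in a risk table and conflict with the operative text.

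**Conclusion.** The concern holds as a mismatch between claim and population. The feasibility conclusion is worded for routinely available tissue, while the single proportion behind it also counts biopsies done solely for research, without limit. The size and direction of any bias are unknown. It is zero if success rates are equal and small if few samples are study-specific, which the routine-first rule in section 6.4 makes possible. The 2 to 10 point range in the brief rests on assumed rates of 60% and 80% and assumed shares of 10% to 50%; none of these is in the protocol. It would go too far to say that the pooled rate is biased upwards, or that the endpoint in section 2.1 is invalid.

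The conflict between section 6.4 and Appendix 1 over previously collected samples is definite and needs no assumption. It leaves open which samples may enter the profile and feasibility sets.

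**What to change.** 1. Record the source of each sample: routine procedure (including surgery and stenting) or study-specific procedure.
2. In section 9.3.2, report the feasibility proportion with an exact 95% CI for routine-procedure samples, alongside the overall rate. Alternatively, keep the single rate and reword the claim in section 2, section 9.3.2 and section 9.5 to biopsies taken at routine or study-specific procedures.
3. Reconcile section 6.4 with Appendix 1 on whether previously collected samples may be used. If they may, give them their own source category and report them separately in the feasibility result.

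The cost is one data field, a few sentences in the protocol and a wider interval for the routine-procedure rate: about 3 to 10 points wider in the cases shown (25.9 − 23.1 = 2.8; 33.1 − 23.1 = 10.0). The rewording option needs no extra data, but gives up the statement about routine tissue.

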## 9.4. Participant population

All samples received of a sufficient quality to perform the tissue analyses will be included.

## 9.5. Procedure(s) to account for missing or spurious data

Samples with failed sample processing at any point (no tumour cells in provided biopsy, failed protein extract preparation, immunoprecipitation or LC-MS/MS analysis) will be withdrawn from the analysis of the primary outcome but incorporated in the secondary outcome regarding the

feasibility of neoantigen identification with the described approach in gastroesophageal adenocarcinoma patients, using routinely available clinical biopsy material.

## **10. DATA MANAGEMENT**

## 10.1. Data collection tools and source document identification

Medical records will be used as source data. The medical record will be flagged to state that the patient is participating in the PROTEAN study.

The PI or delegate will maintain source documents for each participant in the study, consisting of hospital medical records containing demographic and medical information.

An eCRF, using CASTOR Electronic Data Capture system, will be provided by TCTU. The study system will be based on the protocol for the study. Development and validation of the study database and quality control will be done according to TCTU procedures.

The eCRF will not collect more information than is required to meet the aims of the study and to ensure the eligibility and safety of the participant.

The PI may delegate eCRF completion but is responsible for completeness, plausibility and consistency of the eCRF. Delegated study staff will enter the data required by the protocol into the eCRFs following training in the definitions and methods used in completing the eCRF. Any queries will be resolved by the CI or delegated member of the study team. On completion of data collection, the PI must certify that the data entered into the eCRFs is complete and accurate. PI sign-off of the eCRF will be embedded in the eCRF with the PI using their own login.

Data verification, cleaning and extraction of data will be performed as per TCTU local procedures and detailed in the Data Management Plan.

Data preservation and sharing will be in accordance with established procedures at the University of Dundee. All electronic data will be stored on secure University of Dundee or cloud-based servers which have restricted access and have disaster recovery systems in place.

General laboratory data methods and results will be documented in laboratory notebooks and then analysed and written up for publication for dissemination to the scientific community. All electronic data will be stored on password-protected computers in secure staff access - controlled offices at investigator sites. All data and laboratory notebooks will be retained for at least ten years, in accordance with general RCUK guidelines.

## 10.2. Access to Data

The CI, PIs and all institutions involved in the study will permit study-related monitoring, audits, and REC review. In the event of an audit, the CI, PIs and all institutions involved in the study will allow the Sponsor, representatives of the Sponsor or REC direct access to all trial records and source documentation. The company analysing the samples (Platinum Informatics) will have no access to electronic health care records. Data shared with Platinum informatics will be fully anonymised prior to transfer.

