#### III. FUNDING AND SUPPORT IN KIND

FUNDER(S)	FINANCIAL AND NON-FINANCIAL SUPPORT GIVEN
Platinum Informatics,	Funding for the trial.
[name]	Scientific expertise in immunoprecipitation, liquid chromatography-tandem mass spectrometry, and analysis of data to identify tumour neoantigens.

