## 6.8. Storage and analysis of clinical samples

The collection, local processing, storage and transportation of participant samples, including tumour and PBMCs; histopathological quality assurance and processing in the TBR and transportation to Platinum Informatics Ltd. at the School of Life Sciences, University of Dundee, along with return of surplus material to the TBR for storage and additional future analyses, will be detailed in the PROTEAN Clinical Sample Handling Manual, which will be available to all participating sites.

The patient tumour samples and PBMCs (if site is undertaking) will be temporarily stored at the respective collection sites, before transportation to the TBR, at Ninewells Hospital in Dundee.

TBR will catalogue samples and histopathological characterisation and quality assurance checks will be undertaken. Subsequently, tumour specimens will be transported to the School of Life Sciences (SLS), University of Dundee, for neoantigen analysis by Platinum Informatics Ltd. Utilising laboratory facilities at the University of Dundee, SLS, including at the FingerPrints Proteomics and Mass Spectrometry Facility, sample processing, (comprising extract preparation, immunoprecipitation and LC-MS/MS analysis) will be performed according to optimised SOPs established by Platinum Informatics Ltd. Raw MS data will be processed and used by Platinum Informatics for neoantigen identification.

Surplus tumour material will be returned to the TBR for storage and will be available for additional genomic and transcriptomic work, allowing both validation of predicted neoantigens and for additional future proteo-genomic studies undertaken in laboratory facilities at the University of Dundee, SLS with analysis of data undertaken by Platinum Informatics.

PBMC preparations will be used for characterisation of pre-existing T cell responses to identified neoantigens in the Immunoassay Biomarker Core laboratory at Ninewells Hospital and Medical School.

All material will be handled in accordance with the Human Tissue Act 2004 and the 2006 Human Tissue (Scotland). Access to them will be tightly controlled through the CI.

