### 12.11. Access to the final study dataset

The CI and Platinum Informatics will have access to the final study dataset. Access to the final study dataset to others will be approved by the CI.

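### Full anonymisation of data sent to the funder-analyst does not fit the per-participant linkage the study needs, and nothing keeps that company from clinical outcomes before neoantigen calls are final

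*Protocol*

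**What the plan says.** **Status of the data.** Section 10.2 says "The company analysing the samples (Platinum Informatics) will have no access to electronic health care records" and adds "Data shared with Platinum informatics will be fully anonymised prior to transfer".

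**Access.** Section 12.6 limits collated participant data to the CI and appropriately delegated study staff. Section 12.11 says "The CI and Platinum Informatics will have access to the final study dataset" and gives no timing.

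**Roles.** Section III lists the company's contribution as "Funding for the trial". Section 6.8 says "Raw MS data will be processed and used by Platinum Informatics for neoantigen identification", and section 9.3.1 names the company's own proprietary tool, DESIMAL, for this step. Section 9.3 says "The outcome analysis will be performed by the CI, their research team, trial scientific adviser and Platinum Informatics Ltd".

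**Order of work.** Section 9.3 starts the outcome analysis when all samples are in, with "LC-MS/MS immunopeptidome analysis completed and raw MS data generated for subsequent processing".

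**Linkage needed.** Section 2.1 sets T cell responses to the identified neoantigens as the measure for secondary objective 2. For objective 3 it sets correlation of profiles with response, disease control, progression-free survival and overall survival. Section 6.8 places the T cell work in a separate laboratory. Appendix 2 (15.2.1) has sites give each participant a study number.

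**The concern.** There are two problems.

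The first is linkage. Section 1.2 describes neoantigens as largely specific to the patient, so a list is useful only if it returns to the right participant's blood cells and follow-up record. If anonymised means that no key is kept, that return is not possible. If a code is kept, section 10.2 misdescribes the data, and the same description may have been carried into the participant information sheet and the data transfer agreement.

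The second is independence of the calls. Turning spectra into a neoantigen list involves choices of software version and settings. If whoever makes those choices can see who responded or survived, the choices can drift, knowingly or not, towards an association. Here the caller also funds the study and owns the tool. The cohort is 75 participants, and the protocol describes no separate validation set in which a tuned association would be exposed.

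**Working it through.** The protocol gives no figure to reproduce. Section 9.1 says "it is not possible to perform a formal sample size calculation", and no significance level or test is stated. The check is therefore mainly a comparison of text.

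**Step 1: data status against linkage.**
- Objective 2 needs the route company's list → participant → that participant's T cell assay in another laboratory.
- Objective 3 needs the route company's list → participant → response, progression and survival.
- Both routes need an identifier common to the company's output and the study record. The candidates are the study number (15.2.1) and the biorepository's catalogue entry (6.8).
- The protocol does not say that either travels with the samples or data to the company, or who holds a key. Section 10.2, as worded, points the other way.

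**Step 2: access rules against each other.**
- Section 12.6 allows the CI and delegated study staff to see collated data.
- Section 12.11 allows the CI and the company to access the final dataset.
- These agree only if the company counts as delegated study staff. The protocol does not say so, and section V describes delegation logs site by site.
- Sections 10.2 and 12.11 agree only if the final dataset is released to the company in anonymised or coded form. That is not stated either.

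**Step 3: order of calling and outcome analysis.**
- The trigger in section 9.3 is the existence of raw spectra. Their processing comes afterwards.
- The company is named both for the processing (6.8, 9.3.1) and for the outcome analysis (9.3).
- The protocol does not require calls to be fixed, or callers to be kept from outcomes, before clinical data are shared.

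**Step 4: would clinical data exist by then?**
- Inputs: recruitment of 75 over 12 months (9.2), taken as 52 weeks; last visit at week 18 (Appendix 4).
- Assumptions: even recruitment, and the last required sample taken as recruitment closes.
- Participants whose day 1 falls in the first 52 − 18 = 34 weeks have reached week 18 by then: 34/52 × 75 ≈ 49 of 75, if all remain in the study.
- Allowing the 14 days for data entry in 15.2.2: (52 − 18 − 2)/52 × 75 = 32/52 × 75 ≈ 46.
- If later optional samples also count towards all samples being collected, the numbers rise.

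Most of the clinical follow-up would therefore probably exist when processing begins. This shows that the data would be available within the study. It does not show that the company would hold them.

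**Step 5: what is exposed.** Section 9.3.1 describes the primary outcome as qualitative, and it does not use clinical outcomes. Section 9.3.2 labels the profile-outcome analysis exploratory. Only that analysis is open to calls shaped by outcomes. The T cell work is at risk only through the linkage in step 1.

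**The case against.** **The sections can be read together.** Names and record numbers could be removed, a study number or catalogue code kept, and the key held by sites, the trials unit or the biorepository. An analyst can work on such a dataset. This stands as a possible reading. A reader might infer that the sections cannot all hold, or that two secondary objectives are impossible. The documents do not support that, because they never say every key is destroyed. What remains is that section 10.2 does not describe coded data.

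**The company is not said to see outcomes early.** A reader might infer that it receives the final dataset while calls are still being made. Section 12.11 gives no timing, a final dataset would ordinarily contain finished calls, and section 13.2 places analysis and tabulation after study completion. In section 9.3 the outcome analysis also includes the primary outcome, which is the calling itself. The company's named role could be no more than that. This stands: overlap is neither stated nor excluded.

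**A lock belongs in the analysis plan.** Section 9.3 promises a detailed plan before analysis, and transfer terms sit in agreements not at hand. Absence of lock details from the protocol would not by itself be a finding. But the protocol itself fixes the data status, the access rules, the analysts and the trigger. An analysis plan cannot override the first two, and the joint analysis that the protocol states is more open to bias than it needs to be.

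**The size is unknown.** A reader might attach a false-positive rate by supposing several calling settings tested against several outcomes. The number of settings, the significance level and the dependence between tests would all be invented. This objection stands in full.

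**Conclusion.** The point holds in a limited form. Sections 9.3, 10.2, 12.6 and 12.11 need reconciling: full anonymisation, read literally, does not fit the linkage that secondary objectives 2 and 3 require, and no retained code is described. In addition, one company funds the study, owns the tool, makes the calls and shares in the outcome analysis, with nothing in the protocol to keep response or survival data from it until calls are final.

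The second part rests on the absence of a stated safeguard, not on any statement that early access will occur. The consequence is a possible bias in an exploratory analysis, of a size the protocol does not allow anyone to calculate. The primary outcome is not affected by it. The matter should be corrected before data are transferred, but it does not undermine the study.

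**What to change.** - **10.2:** describe data shared with the company as pseudonymised by study number, with the key held outside the company (at sites or the trials unit).
- **12.6 and 12.11:** align them, stating whether the company may see collated data, in what form and from when. Access under 12.11 should begin after the lock below.
- **9.3:** state that the DESIMAL version, its settings and the neoantigen list for each participant are locked and lodged with the trials unit before any response, progression or survival data are released to the company. State that the CI's team runs the association on the locked lists.

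The cost is wording in four sections and one lock step. The participant information sheet and the data transfer agreement must be checked against the pseudonymised status. Neither is available here, so whether they need amending is not known.
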